## 6.1

| Belatacept-Treatment Group Pre-Dialysis    |        |                |                |      |      |      |                  |      |       |      |       |      |                 |      |                 |      |        |      |        |      |
|--|--------|----------------|----------------|------|------|------|------------------|------|-------|------|-------|------|-----------------|------|-----------------|------|--------|------|--------|------|
| Visit #                                    | Screen | 2              | 3              | 4    | 5    | 6    | 7-8              | 9    | 10-11 | 12   | 13-14 | 15   | 16-20           | 21   | 22-26           | 27   | 28-32  | 33   | 34-38  | 39   |
| time points                                |        | 0              | 2              | 1    | 2    | 3    | 4-5              | 6    | 7-8   | 9    | 10-11 | 12   | 13-17           | 18   | 19-23           | 24   | 25-29  | 30   | 31-35  | 36   |
|  |        |                | ± 2            | ± 5  | ± 5  | ± 5  | ± 5              | ± 5  | ± 5   | ± 5  | ± 5   | ± 5  | ± 5             | ± 5  | ± 5             | ± 5  | ± 5    | ± 5  | ± 5    | ± 5  |
|  |        |                | days           | days | days | days | days             | days | days  | days | days  | days | days            | days | days            | days | days   | days | days   | days |
| Eligibility Assessments             |        |                |                |      |      |      |                  |      |       |      |       |      |                 |      |                 |      |        |      |        |      |
| Informed Consent                           | X      |                |                |      |      |      |                  |      |       |      |       |      |                 |      |                 |      |        |      |        |      |
| Inclusion/Exclusion Criteria               | X      |                |                |      |      |      |                  |      |       |      |       |      |                 |      |                 |      |        |      |        |      |
| Medical History                            | X      |                |                |      |      |      |                  |      |       |      |       |      |                 |      |                 |      |        |      |        |      |

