| Safety Assessments                  |        |                |                |      |      |      |                  |      |       |      |       |      |                 |      |                 |      |        |      |        |      |
| Physician Visit                            | X      |                |                | X    | X    | X    |                  | X    |       | X    |       | X    |                 | X    |                 | X    |        | X    |        | X    |
| Physical Examination                       | X      |                |                | X    | X    | X    |                  | X    |       | X    |       | X    |                 | X    |                 | X    |        | X    |        | X    |
| Vital Signs                                | X      | X              | X              | X    | X    | X    | XX               | X    | XX    | X    | XX    | X    | XXXXXX          | X    | XXXXXX          | X    | XXXXXX | X    | XXXXXX | X    |
| Assessment of Signs and Symptoms           |        | X              | X              | X    | X    | X    | XX               | X    | XX    | X    | XX    | X    | XXXXXX          | X    | XXXXXX          | X    | XXXXXX | X    | XXXXXX | X    |
| Adverse Events Assessments                 |        | X              | X              | X    | X    | X    | XX               | X    | XX    | X    | XX    | X    | XXXXXX          | X    | XXXXXX          | X    | XXXXXX | X    | XXXXXX | X    |
| Laboratory Tests                           | X      | X              |                | X    | X    | X    |                  | X    |       | X    |       | X    |                 | X    |                 | X    |        | X    |        | X    |
| EBV/CMV titer                              | X      |                |                |      |      |      |                  |      |       |      |       |      |                 |      |                 |      |        |      |        |      |
| Neurologic Evaluation                      | X      |                |                | X    | X    | X    |                  | X    |       |      |       | X    |                 | X    |                 | X    |        | X    |        | X    |
| Efficacy Assessments                |        |                |                |      |      |      |                  |      |       |      |       |      |                 |      |                 |      |        |      |        |      |

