| DSA/PRA                                    | X      | X              |                | X    | X    | X    |                  | X    |       | X    |       | X    |                 | X    |                 | X    |        | X    |        | X    |
| Mechanistic                         |        |                |                |      |      |      |                  |      |       |      |       |      |                 |      |                 |      |        |      |        |      |
| Sample storage                             | X      | X              | X              | X    | X    | X    | XX               | X    | XX    | X    | XX    | X    | X  | X    | X  | X    | XXXXXX | X    | XXXXXX | X    |
| Clinical Drug Supplies              |        |                |                |      |      |      |                  |      |       |      |       |      |                 |      |                 |      |        |      |        |      |
| Randomize                                  |        | X              |                |      |      |      |                  |      |       |      |       |      |                 |      |                 |      |        |      |        |      |
| Belatacept Infusion            |        | X  | X              | X    | X    | X    | X  X | X    | XX    | X    | XX    | X    | XXXXXX          | X    | XXXXXX          | X    | XXXXXX | X    | XXXXXX | X    |
| Tac/CsA dosing                             |        | X  | X  |      |      |      |                  |      |       |      |       |      |                 |      |                 |      |        |      |        |      |
| Concomitant immunosuppression  |        | X              | X              | X    | X    | X    | XX               | X    | XX    | X    | XX    | X    | XXXXXX          | X    | XXXXXX          | X    | XXXXXX | X    | XXXXXX | X    |

6.1

| Belatacept-Treatment Group Post-Dialysis |           |                        |          |          |          |          |          |          |          |          |          |          |          |                 |          |          |          |          |          |          |          |        |

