|  |  |   |                |   |   |   |   |   |   |   |   |    |   |       |   |       |   |       |   |       |   |       |   |
|--|--|---|----------------|---|---|---|---|---|---|---|---|----|---|-------|---|-------|---|-------|---|-------|---|-------|---|
| Prednisone weaning             |  |   |                | X | X | X |   |   |   |   |   |    |   |       |   |       |   |       |   |       |   |       |   |
| Belatacept Infusion            |  | X | X              | X | X | X | X | X | X | X | X | XX | X | XXXXX | X | XXXXX | X | XXXXX | X | XXXXX | X | XXXXX | X |
| Tac/CsA dosing                             |  |   | X  |   |   |   |   |   |   |   |   |    |   |       |   |       |   |       |   |       |   |       |   |
| Concomitant immunosuppression  |  |   | X              | X |   |   |   |   |   |   |   |    |   |       |   |       |   |       |   |       |   |       |   |

6.1

| Standard of Care Pre-Dialysis               |        |          |          |          |          |          |          |          |          |          |          |          |
|---|--------|----------|----------|----------|----------|----------|----------|----------|----------|----------|----------|----------|
| Visit #                                     | Screen | 2        | 3        | 4        | 5        | 6        | 7        | 8        | 9        | 10       | 11       | 12       |
| time points                                 |        | 0 1mo    | 2mo      | 3mo      | 6mo      | 9mo      | 12mo     | 18mo     | 24mo     | 30 mo    | 36 mo    |          |
|   |        | ± 5 days | ± 5 days | ± 5 days | ± 5 days | ± 5 days | ± 5 days | ± 5 days | ± 5 days | ± 5 days | ± 5 days | ± 5 days |
| Eligibility Assessments              |        |          |          |          |          |          |          |          |          |          |          |          |
| Informed Consent                            | X      |          |          |          |          |          |          |          |          |          |          |          |
| Inclusion/Exclusion Criteria                | X      |          |          |          |          |          |          |          |          |          |          |          |
| Medical History                             | X      |          |          |          |          |          |          |          |          |          |          |          |

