## 6.1

| Standard of Care Post-Dialysis |        |                        |          |          |          |          |          |          |          |          |          |          |          |          |          |          |
|---------------------------------------|--------|------------------------|----------|----------|----------|----------|----------|----------|----------|----------|----------|----------|----------|----------|----------|----------|
| Visit #                        |        | Initiation of Dialysis | 2        | 3        | 4        | 5        | 6        | 7        | 8        | 9        | 10       | 11       | 12       | 13       | 14       | 15       |
| time points                    | Screen |                        | 1mo      | 2mo      | 3mo      | 4mo      | 5mo      | 6mo      | 9mo      | 12mo     | 15mo     | 18mo     | 21mo     | 24mo     | 30mo     | 36mo     |
|                                       |        |                        | ± 5 days | ± 5 days | ± 5 days | ± 5 days | ± 5 days | ± 5 days | ± 5 days | ± 5 days | ± 5 days | ± 5 days | ± 5 days | ± 5 days | ± 5 days | ± 5 days |
| Eligibility Assessments        |        |                        |          |          |          |          |          |          |          |          |          |          |          |          |          |          |
| Informed Consent                      | X      |                        |          |          |          |          |          |          |          |          |          |          |          |          |          |          |
| Inclusion/Exclusion Criteria          | X      |                        |          |          |          |          |          |          |          |          |          |          |          |          |          |          |
| Medical History                       | X      |                        |          |          |          |          |          |          |          |          |          |          |          |          |          |          |
| Safety Assessments             |        |                        |          |          |          |          |          |          |          |          |          |          |          |          |          |          |

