**Secondary Endpoints:**

- Rate of change in GFR
- Time to dialysis measured from the time of randomization to initiation of dialysis
- Overall level of alloantibody as indicated by PRA.
- Incidence of infectious complications.

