Analysis of secondary endpoints will be performed at the end of the study period. Differences in the mean level of allo-antibody (ie PRA) by control and belatacept-treated groups will be compared using a t-test statistic. The rate of decline of GFR among the belatacept group will be compared to the rate of decline of the control group using a Rate Ratio and corresponding 95% Confidence Intervals using the Mantel-Haenszel chi-square test statistic for significance. The time from randomization to initiation of dialysis will be compared between groups using Kaplan-Meier analysis and the log-rank test for significance. The small subset of subjects already requiring dialysis at the time of enrollment will be excluded from this analysis. The incidence of overall infectious episodes will be compared among the belatacept vs. control group by calculating a Risk Ratio and corresponding 95% Confidence Intervals and using the Mantel-Haenszel chi-

square test statistic for significance. For all secondary endpoint analyses, two-tailed  $p < 0.05$  will be considered statistically significant.

Interim analyses will be performed at 18 months to compare the primary endpoint between the belatacept-treated and control groups, using the log-rank test for significance. A two-sided test with a more stringent significance level of 0.001 will be used to preserve the overall significance level of the trial.

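### Infectious episodes are tested with a Risk Ratio that has no stated unit and no person-time, while adverse events are sought far more often in the belatacept arm, so the comparison is open to detection bias against belatacept

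*Combined protocol and SAP*

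**What the plan says.** Sections 2.2 and 8.2 list "Incidence of infectious complications" as a secondary endpoint without defining an episode or a rule for recurrences. Section 8.3.3 then states: "The incidence of overall infectious episodes will be compared among the belatacept vs. control group by calculating a Risk Ratio", with a 95% confidence interval and a Mantel-Haenszel chi-square. For every secondary endpoint, a two-tailed p below 0.05 "will be considered statistically significant". Subject or episode is not specified as the unit, and no person-time denominator is given.

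Table 6.1 has a row for "Adverse Events Assessments" in each schedule:

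- **Belatacept, pre-dialysis:** marked throughout visits 2 to 39 (day 0, week 2, then monthly to month 36).
- **Standard of care, pre-dialysis:** marked at visits 2 to 12, timed at "0 1mo | 2mo | 3mo | 6mo | 9mo | 12mo | 18mo | 24mo | 30 mo | 36 mo".
- **"Belatacept-Treatment Group Post-Dialysis":** marked at dialysis initiation and visits 1 to 37.
- **Standard of care, post-dialysis:** 14 visits after initiation (months 1 to 6, then 9, 12, 15, 18, 21, 24, 30 and 36).

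The EBV/CMV titer row is marked repeatedly for belatacept subjects on dialysis and is empty for controls on dialysis. Section 6.5 (EBV Titers) likewise plans this sampling for belatacept subjects only. The trial is open-label, and Section 8.3 does not mention the unequal schedules.

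**The concern.** Belatacept is infused at the site, so that arm is seen monthly, whereas a pre-dialysis control has 3-month gaps after month 3 and 6-month gaps after month 12. A minor infection that resolved months before the next visit is more likely to go unrecorded in a control. An arm difference can then arise from the calendar alone.

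The undefined unit adds a second problem. Episodes recur within a subject. Comparing them as if independent understates the variance, while reducing them to any infection per subject discards recurrences and may push both arms towards a ceiling. Without person-time, neither reading allows for unequal follow-up. Section 7.7 reduces follow-up after withdrawal to survival, dialysis status and serious events, so non-serious infections are then no longer sought.

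Infection risk under continued immunosuppression is central to the rationale in Section 1.4. A schedule-driven excess would count against belatacept, and a ratio close to its ceiling could hide a real excess.

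**Working it through.** The plan gives no infection rate, precision or power, so there is no figure of its own to reproduce. The inputs are the visit times in Table 6.1. All recall and infection-rate values below are assumptions.

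**1. Visit counts and gaps over 36 months**

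| Schedule | AE visits | Gaps between visits |
|---|---|---|
| Belatacept, pre-dialysis | 39 − 2 + 1 = 38 | 2 × 0.5 month, 35 × 1 month |
| Control, pre-dialysis | 12 − 2 + 1 = 11 | 3 × 1, 3 × 3, 4 × 6 months |
| Belatacept, on dialysis | initiation + 37 = 38 | 2 × 0.5 month, 35 × 1 month |
| Control, on dialysis | 14, or 15 with initiation | 6 × 1, 6 × 3, 2 × 6 months |

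**2. Episode rate ratio when true rates are equal.** Suppose the chance of recording a non-serious infection halves every h months until the next visit. A gap of g months then contributes (h/ln 2)(1 − 2^(−g/h)) recorded months. For h = 6, gaps of 0.5, 1, 3 and 6 months contribute 0.486, 0.944, 2.535 and 4.328:

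- Belatacept: (2 × 0.486 + 35 × 0.944)/36 = 0.945
- Control, pre-dialysis: (3 × 0.944 + 3 × 2.535 + 4 × 4.328)/36 = 0.771
- Control, on dialysis: (6 × 0.944 + 6 × 2.535 + 2 × 4.328)/36 = 0.820

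| h (months) | Belatacept | Control pre | Control on dialysis | Ratio, pre | Ratio, dialysis schedule |
|---|---|---|---|---|---|
| 3 | 0.894 | 0.615 | 0.690 | 1.45 | 1.30 |
| 6 | 0.945 | 0.771 | 0.820 | 1.23 | 1.15 |
| 12 | 0.972 | 0.874 | 0.903 | 1.11 | 1.08 |

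**3. The same bias on subjects with at least one infection.** Assume a true 3-year incidence of 81%, the cyclosporine figure in the Section 1.2.5.2 infection table. The cumulative rate is −ln(0.19) = 1.661, and the recorded risk is 1 − exp(−1.661 × recording probability). On the pre-dialysis schedules:

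| h (months) | Belatacept | Control | Apparent Risk Ratio | Rejection rate at nominal 0.05, 36 per arm |
|---|---|---|---|---|
| 3 | 0.774 | 0.640 | 1.21 | about 24% |
| 6 | 0.792 | 0.722 | 1.10 | about 10% |
| 12 | 0.801 | 0.766 | 1.05 | about 6% |

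At a control incidence of 81% the ratio cannot exceed 1/0.81 = 1.23.

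**4. A different recall model.** Suppose an infection is recorded only if it falls within w months before a visit. The share of follow-up covered is 100% for belatacept throughout. For pre-dialysis controls it is 10/36 = 28% (w = 1), 17/36 = 47% (w = 2), 24/36 = 67% (w = 3) and 100% (w = 6). At w = 6 the apparent ratio is 1.00.

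**5. Effect of the unit.**

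- *Subjects:* a true episode rate ratio of 2 gives a 3-year Risk Ratio of (1 − e^(−6λ))/(1 − e^(−3λ)), which is 1.55, 1.22 or 1.05 for assumed control rates λ of 0.2, 0.5 or 1.0 per year.
- *Episodes treated as independent:* at an assumed 0.5 per year with between-subject (gamma) variance of 0.5 to 1.0, simulated type I error is about 14% to 21%.

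**The case against.** The strongest reply is that a Risk Ratio with a Mantel-Haenszel chi-square is naturally read as subjects with at least one infection. Section 8.3.3 uses Rate Ratio for GFR decline, so it distinguishes the terms. On that reading the statistic is valid and the bias is compressed to 1.21 at most in the cases above. This stands. A reader might infer that a Risk Ratio is simply wrong here; the documents support only that the unit is undefined and that a Risk Ratio does not suit recurrent episodes.

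A reader might also infer that the comparison is certainly biased, or that 38 against 11 holds throughout. Neither is supported:

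- Section 7.3 accepts spontaneous reports, and Section 7.8 tells all subjects to contact a provider promptly for fever or flu-like symptoms. The recall half-lives are assumed.
- Subjects have failing grafts, some enter on dialysis, and controls on dialysis have 14 to 15 assessments.

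The 81% comes from de novo recipients given basiliximab induction. Patients here are at least a year post-transplant, so 1.23 illustrates a ceiling and is not this trial's own.

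Serious infections are not a perfect refuge either. The 24-hour reporting clock starts when staff learn of the event. Section 7.3.1 ends collection 8 weeks after the last investigational product, a point that does not exist for controls.

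Finally, this is one of four secondary endpoints and the primary result is unaffected. That limits the weight of the point, but the infection comparison would still be tested at 0.05 with no allowance for the schedule.

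**Conclusion.** The point holds as a risk that the plan leaves unaddressed. The unequal ascertainment is certain from Table 6.1, and its direction, where it acts, is against belatacept. Its size is not known from the documents. Under recall half-lives of 3 to 12 months, the apparent episode rate ratio is 1.45 to 1.11 on the pre-dialysis schedules and 1.30 to 1.08 against the control dialysis schedule. The apparent per-subject Risk Ratio is 1.21 to 1.05 at an assumed 81% incidence. It is negligible if infections are fully recalled or reported over six months. The belatacept-only EBV/CMV titers on dialysis add asymmetry that these figures do not include. Separately, the missing unit and person-time leave the planned test open to two readings with different properties. The plan should be changed because the remedy is cheap.

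**What to change.** Change the analysis wording in Section 8.3.3, and define an infectious episode and the recurrence rule in Section 8.2:

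1. Make the tested between-arm comparison the proportion of subjects with at least one serious infection. This depends less on visits, though not wholly independent of them. State that SAEs are collected over the same period in both arms.
2. Analyse all episodes as a rate per patient-year, using a negative binomial model or a robust variance.
3. Label the unrestricted all-infection comparison descriptive. Add a sensitivity analysis limited to infections with onset in the month before a visit common to both arms, with matching person-time. Section 7.3 already requires onset to be recorded.

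Do not instead count every infection reported at the common visits. Before dialysis those reports cover 0.5 + 9 × 1 = 9.5 months for belatacept and all 36 for controls. Under the model above that gives a spurious ratio of 0.38, 0.32 or 0.29, a larger distortion in the opposite direction.

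The cost is precision. The prior trials tabulated in Section 1.2.5.2 had serious infections in 36% to 39% by year 3. At an assumed 37.5% in both arms of 36, the standard error of the log Risk Ratio is √(2 × 0.625/13.5) = 0.304, so the 95% limits lie a factor of exp(1.96 × 0.304) = 1.82 either side. At 81% the standard error is √(2 × 0.19/29.16) = 0.114 and the factor is 1.25. No new data or visits are needed.

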## **9 ADMINISTRATIVE SECTION**

### **9.1 Compliance with the Protocol**

The study must be conducted as described in the final IRB/IEC-approved protocol. Documentation of approval, signed by the IRB/IEC chairperson or designee, will be sent to the BMS protocol manager.

All protocol amendments and revisions to the informed consent will be submitted to the BMS protocol manager and to the IRB/IEC. No protocol amendments will be implemented until written approval has been given by the IRB/IEC, except when necessary to eliminate an immediate hazard to study subjects. Administrative letters should also be sent to the BMS protocol manager and IRB/IEC; however, they do not require approval.

If a protocol amendment mandates a revision to the informed consent, the revised consent must be used to obtain consent from subjects currently enrolled in the study if it affects them (eg, if it contains new information regarding safety), and the revised consent must be used to obtain consent from new subjects before enrollment.

